[REDACTED]	[REDACTED]
[REDACTED]	[REDACTED]
C _{max}	Maximum measured concentration of the analyte in plasma
[REDACTED]	[REDACTED]
[REDACTED]	[REDACTED]
[REDACTED]	[REDACTED]
CNS	Central Nervous System
CRF	Case Report Form, paper or electronic (sometimes referred to as 'eCRF')

CSF	Cerebrospinal fluid
CTP	Clinical trial protocol
CTR	Clinical trial report
DILI	Drug induced liver injury
DRESS	Drug reaction with eosinophilia and systemic symptoms
ECG	Electrocardiogram
eCRF	Electronic case report form
eDC	Electronic data capture
EDTA	Ethylenediaminetetraacetic acid
EoTrial	End of trial
EudraCT	European Clinical Trials Database
FAS	Full Analysis Set
GCP	Good Clinical Practice
gCV	Geometric coefficient of variation
GI	Gastro-intestinal
gMean	Geometric mean
GOT	Glutamic oxaloacetic transaminase

[REDACTED]

IB	Investigator's brochure
IEC	Independent Ethics Committee
I _{kr}	Inward rectifier K ⁺ current
IPD	Important protocol deviation
IRB	Institutional Review Board
ISF	Investigator site file

[REDACTED]

LC-MS/MS	Liquid chromatography with tandem mass spectrometry
MCHC	Mean cell haemoglobin concentration
MCV	Mean corpuscular volume
MDA	Methylenedioxyamphetamine
MDMA	Methylenedioxymethamphetamine
MedDRA	Medical Dictionary for Regulatory Activities

[REDACTED]

[REDACTED]

NMDA	N-methyl-D-aspartate
NOAEL	No observed adverse event level
NSFS	Negative Symptom Factor Score
PANSS	Positive and Negative Syndrome Scale

PBPK	Physiologically-based pharmacokinetics
PD	Pharmacodynamic(s)
PE	Polyethylene
PfOS	Powder for reconstitution of an oral solution
PK	Pharmacokinetic(s)
PKS	Pharmacokinetic set
PP	Polypropylene
PR	Pulse rate
qd/QD	once daily
QT	Time between start of the Q-wave and the end of the T-wave in an electrocardiogram
QTc	QT interval corrected for heart rate using the method of Fridericia (QTcF) or Bazett (QTcB)
R	Reference treatment
RDW	Red cell distribution width
REP	Residual effect period
SAE	Serious adverse event
SCR	Screening
SmPC	Summary of Product Characteristics
SOP	Standard operating procedure
T	Test product or treatment
TEAE	Treatment-emergent adverse event
[REDACTED]	[REDACTED]
[REDACTED]	[REDACTED]
[REDACTED]	[REDACTED]
[REDACTED]	[REDACTED]
[REDACTED]	[REDACTED]
[REDACTED]	[REDACTED]
[REDACTED]	[REDACTED]
TSAP	Trial statistical analysis plan
ULN	Upper limit of normal
VAS	Visual analogue scale
[REDACTED]	[REDACTED]
[REDACTED]	[REDACTED]
XTC	Ecstasy

1. INTRODUCTION

BI 425809 is a glycine transporter 1 (GlyT1) inhibitor under development for treatment of cognitive impairment associated with schizophrenia (CIAS).

1.1 MEDICAL BACKGROUND

Schizophrenia is a chronic, severe, and disabling brain disorder affecting both men and women. The disease is characterised by abnormalities in glutamatergic pathways related to N-methyl-D-aspartate (NMDA) receptor hypofunction in cortical and hippocampal brain areas [[R13-4518](#), [R13-4521](#)]. These abnormalities are hypothesised to lead to negative symptoms and cognitive impairment in schizophrenia. Existing treatment options for schizophrenia (i.e. first- and second-generation antipsychotics) primarily affect positive symptoms but have a limited effect on cognitive and negative symptoms [[R15-0595](#)]. Inhibition of GlyT1 aims at improving NMDA receptor hypoactivation by increasing the concentration of the NMDA receptor co-activator glycine in the synaptic cleft.

GlyT1 inhibitors have been tested in healthy volunteers and no serious adverse effects have been noted [[R13-4450](#), [R13-4451](#), [R13-4508](#)]. Proof of clinical concept has been reported for treatment of negative symptoms of schizophrenia in a Phase II clinical trial with the GlyT1 inhibitor Bitopertin (RG1678). In this trial, patients exhibited a larger reduction in the Positive and Negative Syndrome Scale (PANSS) Negative Symptom Factor Score (NSFS) compared with placebo [[R15-1266](#)]. However, subsequent Phase III clinical trials failed to demonstrate a significant effect on negative symptoms of schizophrenia [[R18-1054](#)]. The GlyT1 inhibitor prototype sarcosine also has been shown to improve positive, negative, and cognitive symptoms in patients with schizophrenia [[R13-4447](#), [R13-4524](#)].

1.2 DRUG PROFILE

1.2.1 BI 425809

BI 425809 is a potent and selective inhibitor of GlyT1.

1.2.1.1 Non-clinical drug safety

Proprietary confidential information © 2021 Boehringer Ingelheim International GmbH or one or more of its affiliated companies

For details on the non-clinical pharmacology, pharmacokinetics in animals and toxicology results and for a detailed description of the BI 425809 PK profile please refer to the current IB [c02155957].

[REDACTED]

[figure not shown]
[REDACTED]

[REDACTED]

[REDACTED]

[figure not shown]
[REDACTED]

[REDACTED]

For a more detailed description of the BI 425809 profile, please refer to the current IB [\[c02155957\]](#).

1.2.1.3 Expected exposure of BI 425809 in this trial

1.2.2 Fluconazole

Fluconazole is a triazole antifungal agent. Its primary mode of action is the inhibition of fungal cytochrome P-450-mediated 14 alpha-lanosterol demethylation, an essential step in fungal ergosterol biosynthesis. The accumulation of 14 alpha-methyl sterols correlates with the subsequent loss of ergosterol in the fungal cell membrane and may be responsible for the antifungal activity of fluconazole [[R21-2282](#)].

Pharmacokinetics and drug metabolism

After oral administration fluconazole is well absorbed, and plasma levels (and systemic bioavailability) are over 90% of the levels achieved after intravenous administration. Oral absorption is not affected by concomitant food intake. Peak plasma concentrations in the fasting state occur between 0.5 and 1.5 hours post-dose. Ninety percent steady state levels are reached by day 4-5 with multiple once daily dosing.

Fluconazole achieves good penetration in all body fluids studied. High skin concentration of fluconazole, above serum concentrations, are achieved in the stratum corneum, epidermis-dermis and eccrine sweat. Fluconazole accumulates in the stratum corneum.

Fluconazole is metabolised only to a minor extent. Plasma elimination half-life for fluconazole is approximately 30 hours. The major route of excretion is renal, with approximately 80% of the administered dose appearing in the urine as unchanged medicinal product. Fluconazole clearance is proportional to creatinine clearance. There is no evidence of circulating metabolites.

Fluconazole is a moderate inhibitor of the isozymes CYP2C9 and CYP3A4: Concomitant intake of fluconazole 200 mg and midazolam (a CYP3A4 substrate) 7.5 mg orally increased the midazolam AUC and half-life 3.7-fold and 2.2-fold, respectively [[R21-2282](#)], similar results were found in [[R03-2551](#)]. Fluconazole is also a strong inhibitor of the isozyme CYP2C19 [[R21-2282](#)].

Clinical safety in healthy volunteers:

For an overview of safety when fluconazole was used as a moderate inhibitor in healthy volunteer trials, a number of publications is cited here which use different treatment schedules for fluconazole ranging from

- administration of fluconazole (400 mg on day 1 and 200 mg qd on subsequent days) over 4 days in Scott et al. [[R21-2438](#)], over 7 days in Gupta et al. [[R21-2439](#)] or over 20 days in Gardin et al. [[R21-2467](#)],
- administration of fluconazole (400 mg qd) over 6 days in Mueck et al. [[R13-3004](#)] to
- administration of fluconazole (400 mg qd) over 11 days in Poggesi et al. [[R21-2461](#)] and Brings et al. [[R21-2447](#)], the latter including a loading dose of 800 mg fluconazole.

In these studies, fluconazole was - overall - safe and well tolerated. The adverse event most often described was headache of mostly mild, sometimes moderate intensity. However, due to the study designs, where other drugs under investigation were co-administered with fluconazole, proof of causality is challenging. Please find a more detailed description of the safety observed in the cited trials below.

- Scott et al. [[R21-2438](#)]: Trial medication lumiracoxib and fluconazole; 13 subjects included, 1 adverse event (headache in a subject receiving lumiracoxib plus fluconazole), starting 10 days after study drug administration, not considered drug-related
- Gupta et al. [[R21-2439](#)]: Trial medication tofacitinib and fluconazole; 12 subjects included, a total of six subjects reported 15 AEs. All were mild with the exception of 1 moderate case of headache during fluconazole treatment. The most frequently reported

treatment-emergent, all-causality AE was headache (reported in four subjects). No deaths, severe AEs, SAEs or discontinuations. No clinically important changes in vital signs, clinical laboratory parameters or ECG.

- Gardin et al. [R21-2467]: Trial medication siponimod and fluconazole; 14 subjects enrolled of which 11 completed the study, two withdrew consent, and one discontinued due to an upper respiratory tract infection. In period 1 (siponimod alone), 11 subjects (79%) experienced AEs compared with eight subjects (73%) in period 2 (Siponimod + fluconazole). The most commonly reported AEs ($\geq 10\%$ of subjects) were headache, dizziness, somnolence, bradycardia, fatigue, seasonal allergy, and upper respiratory tract infection. The majority of AEs reported in the study were of mild intensity. The AEs of moderate intensity reported in the treatment groups were bradycardia and abdominal discomfort (siponimod alone) and headache and disturbance in attention (siponimod + fluconazole), all of which were resolved without any treatment. No deaths or SAEs were reported during the study. No clinically significant changes were observed in vital signs throughout the study. The most common ECG abnormality observed during the study was bradycardia. None of these events were considered clinically significant.
- Poggesi et al. [R21-2461]: Trial medication erdafitinib and fluconazole; a total of 13/18 subjects experienced at least one treatment-emergent adverse event (TEAE), the most commonly reported one was headache. All TEAEs were Grade 1 or 2 in severity, no serious TEAE reported, no clinically significant laboratory safety abnormalities, no clinically meaningful ECG, physical examination, or vital signs observations reported during the study.
- Brings et al. [R21-2447]: Trial medication rivaroxaban, ciclosporin and fluconazole; 12 subjects included. Non-serious adverse events with possible, probable, or certain causal relationship to the trial drugs were hypomagnesemia (n=9), dry mouth (n=3), sensation of heat or cold in hands or feet (n=3), decline in plasma magnesium not reaching criteria for hypomagnesemia (n=2), headache (n=2), gastric pain (n=1), heartburn (n=1), muscle ache (n=1), flank pain (n=1), pruritic lower arm exanthema (n=1), hypertrichosis (n=1), hyperkalemia (n=1), isolated increase in bilirubin (n=1), increase in creatine kinase (CK) and glutamic oxaloacetic transaminase (GOT) (n=1), anemia (n=1). All adverse events were mild and resolved or were resolving at the end of trial.

QTcF increased during fluconazole by 11.4 ± 6.0 ms (range 5-23 ms, $P < 0.01$). QTcF or relative change in QTcF did not correlate with fluconazole concentration. However, in the present trial ECGs were done primarily for safety reasons and not to evaluate effects on QTc. Thus, the authors obtained only single ECG recordings, the screening ECG could be obtained later in the day, and participants were not required to be fasting at screening and on the fifth day of fluconazole. Thus, also circadian variability or food effects may have influenced QTc.

Clinical safety in patients:

According to the German “Fachinformation”, the most frequently ($\geq 1/100$ to $< 1/10$) reported adverse reactions are headache, abdominal pain, diarrhoea, nausea, vomiting, alanine aminotransferase increased, aspartate aminotransferase increased, blood alkaline phosphatase increased and rash (see also Section [1.4.3.2](#)).

Fluconazole (Diflucan[®]) has been associated with rare cases of serious hepatic toxicity including fatalities, primarily in patients with serious underlying medical conditions. In cases of fluconazole associated hepatotoxicity, no obvious relationship to total daily dose, duration of therapy, sex or age of patient has been observed. Fluconazole hepatotoxicity has usually been reversible on discontinuation of therapy.

Fluconazole causes QT prolongation via the inhibition of Rectifier Potassium Channel current (I_{Kr}). During post-marketing surveillance, there have been very rare cases of QT prolongation and torsades de pointes in patients taking Diflucan. These reports included seriously ill patients with multiple confounding risk factors, such as structural heart disease, electrolyte abnormalities and concomitant treatment that may have been contributory.

Fluconazole 200 mg to 400 mg daily has no clinically significant effect on endogenous steroid levels or on ACTH stimulated response in healthy male volunteers.

For a detailed description of the fluconazole profile, please refer to the German ‘Fachinformation’ [[R21-2282](#)].

1.2.3 Residual Effect Period

[REDACTED]

1.3 RATIONALE FOR PERFORMING THE TRIAL

[REDACTED]

1.4 BENEFIT - RISK ASSESSMENT

1.4.1 Expected benefit for the target population

Participation in this clinical trial is without any (therapeutic) benefit for healthy subjects. Their participation, however, is of major importance for the development of BI 425809 which

may help to treat patients suffering from CIAS. Subjects are exposed to risks of study procedures and risks related to the exposure to the trial medication.

1.4.2 Procedure-related risks

The use of an indwelling venous catheter or venepuncture for e.g. blood sampling may result in mild bruising, and in rare cases, in transient inflammation of the wall of the vein, or nerve injury, potentially resulting in paraesthesia, reduced sensibility, and/or pain for an indefinite period.

ECG electrodes may cause local and typically transient skin reactions.

The total volume of blood withdrawn per subject during the entire study will not exceed the volume of a normal blood donation (500 mL). No health-related risk to healthy subjects is expected from withdrawal of this volume of blood.

1.4.3 Drug-related risks and safety measures

1.4.3.1 Risks related to the administration of BI 425809

For clinical safety in healthy subjects observed so far upon administration of BI 425809 please refer to Section 1.2.1.2. [REDACTED]

[illegible]

1.4.3.2 Risks related to the administration of fluconazole

Fluconazole (Diflucan[®]) is a market-approved drug. The dose used in this trial (400 mg qd for 13 days) is within the therapeutic range used for patients to treat fungal infections [[R21-2282](#)].

Based on the German ‘Fachinformation’ for Diflucan[®], the following adverse reactions have been observed and reported during treatment with Diflucan with the following frequencies: Very common ($\geq 1/10$); common ($\geq 1/100$ to $< 1/10$); uncommon ($\geq 1/1,000$ to $< 1/100$); rare ($\geq 1/10,000$ to $< 1/1,000$); very rare ($< 1/10,000$), not known (cannot be estimated from the available data).

- Common: Headache, abdominal pain, vomiting, diarrhea, nausea, alanine aminotransferase increased, aspartate aminotransferase increased, blood alkaline phosphatase increased, rash
- Uncommon: Anaemia, decreased appetite, somnolence, insomnia, seizures, paraesthesia, dizziness, taste perversion, vertigo, constipation, dyspepsia, flatulence, dry mouth, cholestasis, jaundice, bilirubin increased, drug eruption, urticarial, pruritus, increased sweating, myalgia, fatigue, malaise, asthenia, fever
- Rare: Agranulocytosis, leukopenia, thrombocytopenia, neutropenia, anaphylaxis, hypercholesterolaemia, hypertriglyceridaemia, hypokalemia, tremor, torsade de pointes, QT prolongation, hepatic failure, hepatocellular necrosis, hepatitis, hepatocellular damage, toxic epidermal necrolysis, Stevens-Johnson syndrome, acute generalized exanthematous-pustulosis, dermatitis exfoliative, angioedema, face oedema, alopecia
- Not known: Drug reaction with eosinophilia and systemic symptoms (DRESS)

Risk mitigation hepatic injury:

- During fluconazole dosing phase laboratory liver parameters will be regularly assessed
- Only subjects with liver parameters AST, ALT and GGT within normal range will be allowed to participate in the trial (see Section [3.3.3](#))
- In case of relevant increase in liver enzymes or hepatic injury (DILI), subjects will discontinue trial treatment (see Section [3.3.4.1](#))

Risk mitigation QT prolongation:

- Subjects with baseline disease (such as pro-arrhythmic conditions) will be excluded from the trial
- No concomitant therapy prolonging the QT interval will be allowed
- During fluconazole dosing phase ECG will be assessed regularly for potential QT prolongation
- Laboratory tests (including determination of potassium levels) will be performed

Risk mitigation dermatological reaction:

- In case a rash occurs during the fluconazole dosing phase which is attributable to fluconazole treatment, the respective subject will discontinue study treatment (see Section [3.3.4.1](#))

For further risks and side-effects associated with the administration of Diflucan[®] please refer to the German 'Fachinformation' [[R21-2282](#)].

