5.2.3 Safety laboratory parameters

For the assessment of laboratory parameters, blood and urine samples will be collected by the trial site at the times indicated in the Flow Chart after the subjects have fasted for at least 10 h. For retests, at the discretion of the investigator or designee, overnight fasting is not required. Fasting is not required for safety lab C (see Flow Chart and Table [5.2.3: 1](#)).

The parameters that will be determined are listed in Tables 5.2.3: 1 and [5.2.3: 2](#). Reference ranges will be provided in the ISF, Section 10.

Manual differential white blood cell count or urine sediment examinations will only be performed if there is an abnormality in the automatic blood cell count or in the urinalysis, respectively.

Table 5.2.3: 1 Routine laboratory tests

Functional lab group	BI test name [comment/abbreviation]	A ¹	B ¹	C ¹	D ¹
Haematology	Haematocrit	X	X	--	X
	Haemoglobin	X	X	--	X
	Red Blood Cell Count/Erythrocytes	X	X	--	X
	Reticulocytes, absol.	X	--	--	X
	Reticulocytes/Erythrocyte	X	--	--	X
	White Blood Cells/Leucocytes	X	X	--	X
	Platelet Count/Thrombocytes (quant)	X	X	--	X
Automatic WBC differential, relative	Neutrophils/Leukocytes; Eosinophils/Leukocytes; Basophils/Leukocytes; Monocytes/Leukocytes; Lymphocytes/Leukocytes	X	X	--	X
Automatic WBC differential, absolute	Neutrophil, absol.; Eosinophils, absol.; Basophils, absol.; Monocytes, absol.; Lymphocytes, absol.	X	X	--	X
Manual differential WBC (if automatic differential WBC is abnormal)	Neut. Poly (segs); Neut. Poly (segs), absol.; Neutrophils Bands; Neutrophils Bands, absol.; Eosinophils/Leukocytes; Eosinophils, absol.; Basophils/Leukocytes; Basophils, absol.; Monocytes/Leukocytes; Monocytes, absol.; Lymphocytes/Leukocytes; Lymphocytes, absol.				
Coagulation	Activated Partial Thromboplastin Time	X	X	--	X
	Prothrombin time – INR (International Normalization Ratio)	X	X	--	X
Enzymes	AST [Aspartate transaminase] /GOT, SGOT	X	X	X	X
	ALT [Alanine transaminase] /GPT, SGPT	X	X	X	X
	Alkaline Phosphatase	X	X	X	X
	Gamma-Glutamyl Transferase	X	X	X	X
	Creatine Kinase [CK]	X	--	--	--
	Creatine Kinase Isoenzyme MB [only if CK is elevated]	X	--	--	--
Hormones	Thyroid Stimulating Hormone	X	--	--	--
Substrates	Glucose (Plasma)	X	X	--	X
	Creatinine	X	X	--	X
	GFR/ CKD-EPI ³	X	--	--	--
	Bilirubin, Total	X	X	--	X
	Bilirubin, Direct	X	X	--	X
	Protein, Total	X	X	--	X
	C-Reactive Protein (Quant)	X	X	--	X
Electrolytes	Sodium	X	X	--	X
	Potassium	X	X	--	X

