5.2.4 Electrocardiogram

Twelve-lead ECGs (I, II, III, aVR, aVL, aVF, V1 - V6) will be recorded using a computerised electrocardiograph ([REDACTED]) at the times provided in the [Flow Chart](#).

To achieve a stable heart rate at rest and to assure high quality recordings, the site personnel will be instructed to assure a relaxed and quiet environment, so that all subjects are at complete rest.

All ECGs will be recorded for a 10 sec duration after subjects have rested for at least 5 min in a supine position. ECG assessment will always precede all other study procedures scheduled for the same time to avoid compromising ECG quality.

All ECGs will be stored electronically on the Muse CV Cardiology System ([REDACTED]) ([REDACTED]). Electrode placement will be performed according to the

method of Wilson, Goldberger and Einthoven modified by Mason and Likar (hips and shoulders instead of ankles and wrists).

All locally printed ECGs will be evaluated by the investigator or a designee. Abnormal findings will be reported as AEs (during the trial) or baseline conditions (at screening) if assessed to be clinically relevant by the investigator. Any ECG abnormalities will be carefully monitored and, if necessary, the subject will be removed from the trial and will receive the appropriate medical treatment.

ECGs may be repeated for quality reasons (for instance, due to alternating current artefacts, muscle movements, or electrode dislocation) and the repeated ECG will be used for analysis. Additional (unscheduled) ECGs may be collected by the investigator for safety reasons.

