## **6. GENERAL ANALYSIS DEFINITIONS**

### **6.1 TREATMENTS**

For basic study information on the treatment to be administered, and selection of dose, cf. Section 4 of the CTP.

Subjects will receive the following two treatments in a fixed sequence (reference treatment always followed by test treatment).

In Period Reference R, all subjects will receive 1 tablet containing

- 10 mg BI 425809 (Reference Treatment R) as a single dose

Afterwards, in Period Test T, all subjects will receive

- 2 capsules, each containing 200 mg Fluconazole, once daily for 13 days (Day -4 to Day 9) and 1 tablet containing 10 mg BI 425809 as a single dose on Day 1 (Test Treatment T).

For statistical analysis of AEs, the following analysis phases are defined for each subject.

Table 6.1: 1 Analysis phases for statistical analysis of AEs, and actual treatment for analysis of laboratory data and vital signs

Study analysis phase	Label	Start	End
Screening 	Screening	Date of informed consent	Date/time of first administration of BI 425809
On treatment	BI 425809	Date/time of first administration of BI 425809	Date/time of first administration of BI 425809 + REP (11 days) or 12:00 a.m. on day after last contact date (whichever occurs first)
Follow-up	F/U BI 425809	Date/time of first administration of BI 425809 + REP (11 days)	Date/time of first administration of Fluconazole or 12:00 a.m. on day after last contact date (whichever occurs first)
On treatment	Fluconazole	Date/time of first administration of Fluconazole	Date/time of second administration of BI 425809 or 12:00 a.m. on day after last contact date (whichever occurs first)
On treatment	BI + Fluconazole	Date/time of second administration of BI 425809	Date/time of second administration of BI 425809 + REP (14 days) or 12:00 a.m. on day after last contact date (whichever occurs first)
Follow-up	F/U BI + Fluconazole	Date/time of second administration of BI 425809 + REP (14 days)	12:00 a.m. on day after last contact date

 See [Section 6.7](#) for definition of baseline, which will be used in the statistical analyses of safety laboratory data and vital signs.

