The on-treatment phase for 'BI + Fluconazole' includes both the REP for BI 425809 (14 days) and Fluconazole (6 days). Since the second administration of BI 425809 is scheduled at 9:00 am on Visit 3, Day 1, while the last administration of Fluconazole is scheduled at 8:00 am on the Visit 3, Day 9 (see CTP, Flow chart). Therefore, Date/time of the second administration of BI 425809 + REP (14 days) is one hour after Date/time of the last administration of Fluconazole + REP (6 days).

AE summary tables will present results for the on-treatment phases only. All AEs will be listed.

In AE tables in CTR Section 15.3 (but not in Appendix 16.1.13.1.8.1 and Appendix 16.1.13.1.8.2 AE tables), the following totals will be provided in addition:

- **"Total BI"**, defined as the total over all on-treatment phases involving BI 425809
- **"Total Fluconazole"**, defined as the total over all on-treatment phases involving Fluconazole
- **"Total on-trt"**, defined as the total over all on-treatment phases

Safety laboratory data, vital signs and PK parameters will be analyzed based on treatment periods (BI 425809 and BI+Fluconazole) with clear differentiation between baseline (cf. [Section 6.7](#)) and post-baseline measurements. Measurements will be considered on-treatment, if they were taken within the on-treatment phases of BI 425809 or BI+Fluconazole as defined in [Table 6.1: 1](#). More details on the technical implementation of these analyses are provided in the ADS Plan of this TSAP.

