## **6.7 BASELINE, TIME WINDOWS AND CALCULATED VISITS**

For both periods, the last available value determined prior to administration of BI 425809 will be defined as baseline.

Time windows are defined in Section 6.1 of the CTP. Adherence to time windows will be checked at the Report Planning Meeting.

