### 7.8.2 Laboratory data

The analyses of laboratory data will be descriptive in nature and will be based on BI standards "Display and Analysis of Laboratory Data" (9).

Analyses will be based on normalised values, which means transforming to a standard unit and a standard reference range. The original values will be analysed if the transformation into standard unit is not possible for a parameter.

Descriptive statistics of laboratory values over time and for the difference from baseline (see Section 6.7) will be provided. Frequency tables of changes between baseline and last value on treatment with respect to the reference range will be presented.

Unscheduled measurements of laboratory data will be assumed to be repeat measurements of the most recent scheduled measurement (e.g. for follow-up or confirmation of a particular

value). Therefore, unscheduled measurements will be assigned to the planned time point of the previous scheduled measurement. Descriptive statistics will be calculated by planned time point based on the worst value of the subject at that planned time point (or assigned to that planned time point).

Clinically significant abnormal laboratory values are only those identified either in the Investigator's comments or at the Report Planning Meeting at the latest. It is the Investigator's responsibility to decide whether a lab value is clinically significant abnormal or not.

Laboratory data will be compared to their reference ranges. Values outside the reference range as well as possibly clinically significant values will be highlighted in the listings. Possibly clinically significant laboratory values will be listed in Section 15.4.1.

Clinically relevant findings in laboratory data will be reported as baseline conditions (prior to first administration of study treatment) or as AEs (after first administration of study treatment) if judged clinically relevant by the investigator, and will be analyzed as such.

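### Safety laboratory set C omits potassium, so the last planned on-dosing potassium in Treatment T is Day 2, before seven of the 13 fluconazole doses and the Day 8 ECG

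*Protocol*

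**What the plan says.** Protocol Section 1.2.2 states that fluconazole prolongs QT. It describes post-marketing torsade reports in patients with confounding factors, "such as structural heart disease, electrolyte abnormalities and concomitant treatment that may have been contributory". Exclusion criterion 21 treats hypokalaemia as a torsade risk factor at entry. Section 1.4.3.2 lists hypokalaemia, QT prolongation and torsade de pointes as rare reactions. Its QT mitigation list includes regular ECGs during fluconazole dosing and, as a separate item, "Laboratory tests (including determination of potassium levels) will be performed".

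In Table 5.2.3: 1 (columns A, B, C, D) the potassium row reads "Potassium X X -- X". Set C contains only AST, ALT, alkaline phosphatase and GGT.

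The Flow Chart plans, for Treatment T, set C on Day -1, set B on Days 1 and 2, set C on Days 4, 6 and 8, and set D at the end-of-trial visit (Days 16 to 30). ECGs fall on Days -4, 1, 2 and 8 and at end of trial. Treatment R has set B on Days 1 and 2 and set C on Day 10.

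SAP Section 7.8.2 plans "Frequency tables of changes between baseline and last value on treatment". SAP Section 6.7 says that in each period "the last available value determined prior to administration of BI 425809 will be defined as baseline". SAP Section 6.1 adds: "Measurements will be considered on-treatment, if they were taken within the on-treatment phases of BI 425809 or BI+Fluconazole". Table 6.1: 1 ends those phases 11 days after the first BI 425809 dose and 14 days after the second.

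**The concern.** The protocol names potassium as one of its QT safeguards, yet the panel used from Day 4 onwards does not contain it. Day 8 is the only ECG planned after Day 2 while dosing continues, and it is the on-drug ECG with the longest fluconazole exposure. If it showed a change, the investigator would need an unscheduled potassium test to interpret it. In the report, a subject who completed dosing with scheduled tests only would contribute no potassium value from Days 3 to 9. That subject's Treatment T potassium shift would compare two values about a day apart, both on fluconazole. What is at stake is the completeness of a safety measure; the PK endpoints are unaffected.

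**Working it through.** **Dose count.** Doses fall on Days -4 to -1 and Days 1 to 9 (no Day 0): 4 + 9 = 13. This matches the 13 days in Protocol Section 4.1.1.

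**Schedule in Treatment T** (Flow Chart and Table 5.2.3: 1; a dose planned for the same time as the assessment is not counted as given):

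| Day (time) | Set | Potassium | ECG | Doses already given |
|---|---|---|---|---|
| -4 (-97:00) | none | no | yes | 0 |
| -1 (-25:00) | C | no | no | 3 |
| 1 (-2:00) | B | yes | yes | 4 |
| 2 (24:00) | B | yes | yes | 6 |
| 4 (71:00) | C | no | no | 7 |
| 6 (119:00) | C | no | no | 9 |
| 8 (167:00) | C | no | yes | 11 |
| 16 to 30 | D | yes | yes | 13 |

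The Day -4 ECG is a pre-drug recording, since under Section 5.2.4 "ECG assessment will always precede all other study procedures scheduled for the same time". The on-drug ECGs are therefore Days 1, 2 and 8, and only Day 8 lacks a same-day potassium.

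**Coverage now.**
- Doses after the last on-dosing potassium: 13 - 6 = 7 (Days 3 to 9). The laboratory window of ±45 min does not alter this, because the earliest Day 2 draw is 23:15 and the Day 2 dose is at 23:00.
- Last potassium to Day 8 ECG: 167 - 24 = 143 h.
- Last potassium to last dose: 191 - 24 = 167 h.

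**SAP shift now.**
- The Treatment T on-treatment phase ends on Day 1 09:00 + 14 days = Day 15 09:00. Set D is on Day 16 at the earliest, so it is excluded.
- Treatment T potassium shift: 24 - (-2) = 26 h, after 4 versus 6 doses.
- Treatment R potassium shift: 24 - (-2) = 26 h.
- The four set C enzymes run to Day 8 in Treatment T. The Day 2 end applies to potassium and other analytes outside set C.

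**With potassium in every set C draw.**
- Potassium time points during dosing rise from 2 to 6 (Days -1, 1, 2, 4, 6, 8).
- Intervals from Day 2 to the last dose: 71 - 24 = 47 h, 119 - 71 = 48 h, 167 - 119 = 48 h, 191 - 167 = 24 h.
- Doses after the last value: 2 (Days 8 and 9), assuming set C is drawn with the PK sample before the Day 8 dose.
- Treatment T shift: 167 - (-2) = 169 h, after 4 versus 11 doses.
- Treatment R shift: 215 - (-2) = 217 h. Day 10 lies inside the 11-day phase, which ends on Day 12.

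**Closeness to steady state.** With the 30 h half-life in Section 1.2.2, the fraction reached after n daily doses is 1 - 2^(-24n/30).
- n = 4: 1 - 2^(-96/30) = 89%.
- n = 6: 1 - 2^(-144/30) = 96%.

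This agrees with the protocol's statement that 90% is reached by day 4 to 5.

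**Size of the risk.** The rare band is 1/10,000 to under 1/1,000. In 15 subjects that is 15 × 1/10,000 = 0.0015 to under 15 × 1/1,000 = 0.015 expected cases over the whole course, and only part of that after Day 2.

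**The case against.** The strongest reply is that the plan does what it says. Section 1.4.3.2 attaches a regular schedule during dosing to liver parameters and to ECG, but not to potassium. Potassium is measured at screening, on Days 1 and 2 of both periods and at end of trial, and set C is a liver panel serving a different bullet. That stands. A reader might infer that the protocol contradicts its own mitigation, and the text does not support that.

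A reader might also infer that no potassium can appear from Days 3 to 9, or that the shift table can never show a later fall. That goes too far. Sections 3.3.4 and 6.2.3 call for an end-of-trial examination at early discontinuation, which includes set D. Unscheduled tests are allowed, and values before Day 15 09:00 count as on-treatment. The limitation concerns completers with scheduled tests only. Unscheduled tests are a partial answer, since they depend on someone seeing a reason to test. SAP Section 7.8.2 also assigns them to the previous planned time point, so a later potassium could be tabulated under Day 2 if that rule is applied analyte by analyte.

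The remedy has real drawbacks. The Treatment R and T potassium shifts now span the same 26 h; afterwards they would span 217 h and 169 h, so the change does not improve their match. Set B is drawn fasted and set C need not be. The Treatment T baseline remains a value taken on fluconazole.

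Materiality is low: the subjects are healthy men, torsade risk factors are excluded, QT-prolonging drugs are banned, AEs are asked about on each dosing day, and Days 1 and 2 already sample near steady state. The SAP plans no ECG analysis that would use a paired potassium. These points limit the size of the gain. They do not put a potassium value beside the Day 8 ECG.

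**Conclusion.** The gap is real, but it is a low-materiality improvement to consider. It is neither an error nor a broken commitment. For subjects who complete dosing and have scheduled tests only, potassium monitoring in Treatment T stops at Day 2, with 7 of 13 doses still to come. The one later on-drug ECG has no same-day potassium, and the potassium shift covers 26 h with both values on fluconazole. The shift table as a whole does not stop at Day 2, because the liver enzymes in set C continue to Day 8.

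The counts follow directly from the Flow Chart and Table 5.2.3: 1. The risk figure assumes that the listed frequency band applies to these 15 subjects. The near-steady-state figures assume simple accumulation at a 30 h half-life; they show that early exposure is well sampled, but not that potassium stays stable over the following week. What favours a change is its low cost.

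**What to change.** Add potassium to set C in Table 5.2.3: 1 for all set C draws: Treatment T Days -1, 4, 6 and 8, and Treatment R Day 10. This gives the Day 8 ECG a same-day value and extends on-treatment potassium to Day 8 in Treatment T and Day 10 in Treatment R.

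The cost is 5 × 15 = 75 determinations, with no new visit or venepuncture if the set C tube volume suffices. It needs a protocol amendment, with ethics committee and competent authority approval before implementation (Section 8.1).

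Restricting the change to Treatment T Days 4, 6 and 8 would cost 3 × 15 = 45 determinations, but it would leave shift spans of 26 h in Treatment R against 169 h in Treatment T. Changing all of set C is therefore preferable. The report should state the remaining limits: unequal spans (217 h and 169 h), possibly non-fasted later values, and an on-fluconazole baseline in Treatment T.
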